8.2.3. Palm/Sole Assessment

Thickening of the skin on the palms and soles will be measured on a 5-point scale at all clinic visits. The scoring is as follows in [Table 7](#).

Table 7: Palm/Sole Scoring Definitions

Score	Definition
0	Clear: No thickening, no roughness, no fissure
1	Almost clear: Only slight thickening, minimal to no roughness, no fissures
2	Mild: Some thickening, mild roughness on palpation, few fissures may be present
3	Moderate: Substantial and diffuse thickening, coarse roughness on palpation may be present, fissures may be present
4	Severe: Very thickened and rough skin, numerous fissures

The change from baseline palm/sole assessment score will be analyzed using an MMRM. The MMRM model will include change from baseline in palm/sole assessment score as the dependent variable, treatment, study visit, treatment-by-visit interaction, and age group as fixed effects, subject as a random effect, and baseline palm/sole assessment score as a covariate. All post-baseline study visits will be included in the model; however, the primary comparison will be between the active trifarotene cream HE1 groups and vehicle at Day 90. An unstructured covariance matrix will be used to model the within-subject errors. The Kenward-Roger approximation will be used to estimate degrees of freedom. In case of convergence issues, other covariance structures will be explored including AR(1), CS, and VC with each model fit to find the covariance structure with the best fit. The fit statistics will be compared for all covariance structures; the structure with the smallest Akaike information criterion will be retained as the preferred model and noted in the resulting table. For the OLE period, the model will not include treatment or treatment-by-visit interaction since all subjects receive the same treatment in the OLE.

The LS mean change from baseline will be presented along with the associated 95% CI within each treatment group. The overall P value of the model will be presented to test the null hypothesis that the change from baseline to subsequent study visit is 0 with a 2-sided alternative considering a difference in either direction.

In comparing treatments (active trifarotene cream HE1 groups minus vehicle), LS mean differences in change from baseline will be presented along with associated 95% CIs and P values. The null hypothesis that the difference in change from baseline in active trifarotene cream HE1 groups minus control vehicle is 0 with a 2-sided alternative considering a difference in either direction.

The observed value and change from baseline in palm/sole assessment score will also be summarized descriptively by study visit and treatment group using descriptive statistics in addition to the above noted model for the Double-blind Period and OLE.

Additionally, the proportion of subjects who experience a 2-grade change from baseline to Day 90 in palm/sole assessment score will be summarized by treatment group and analyzed using a logistic regression model with treatment, baseline palm/sole assessment score, and age group as factors. The odds ratios and 95% CIs for the odds ratios will be presented. The difference in proportions between the active trifarotene cream HE1 groups and vehicle cream group, 95% CIs for the differences, and P values for the differences in treatment will also be presented.

The potential for heterogeneity of treatment effects will be assessed by testing treatment-by-factor interactions. The logistic regression model for the analysis will be expanded to include the treatment-by-age group interaction. In the event of quasi or complete separation, the logistic regression model will use Firth's penalized maximum likelihood estimation.

8.2.4. Quality of life per Dermatology Life Quality Index (DLQI) and Children's DLQI (cDLQI)

The DLQI is a dermatology-specific Quality of Life instrument for subjects aged 17 years and older. The cDLQI is for subjects aged 12 to 16 years. It is a 10-question validated questionnaire with 6 domains: symptoms and feelings, daily activities, leisure, work and school, personal relationships, and treatment. Higher scores indicate poorer quality of life. The investigator will use his or her judgment of the maturity of the subject to decide which version of the questionnaire to use; the same version will be used for the subject throughout the study.

The change from baseline DLQI/cDLQI score will be analyzed using an MMRM. The MMRM model will include change from baseline in DLQI/cDLQI score as the dependent variable, treatment, study visit, and treatment-by-visit interaction as fixed effects, subject as a random effect, and baseline DLQI/cDLQI score as a covariate. All post-baseline study visits will be included in the model; however, the primary comparison will be between the active trifarotene cream HE1 groups and vehicle at Day 90. An unstructured covariance matrix will be used to model the within-subject errors. The Kenward-Roger approximation will be used to estimate degrees of freedom. In case of convergence issues, other covariance structures will be explored including AR(1), CS, and VC with each model fit to find the covariance structure with the best fit. The fit statistics will be compared for all covariance structures; the structure with the smallest Akaike information criterion will be retained as the preferred model and noted in the resulting table.

The LS mean change from baseline will be presented along with the associated 95% CI within each treatment group. The overall *P* value of the model will be presented to test the null hypothesis that the change from baseline to subsequent study visit is 0 with a 2-sided alternative considering a difference in either direction.

In comparing treatments (active trifarotene cream HE1 groups minus vehicle), LS mean differences in change from baseline will be presented along with associated 95% CIs and *P* values. The null hypothesis that the difference in change from baseline in active trifarotene cream HE1 groups minus control vehicle is 0 with a 2-sided alternative considering a difference in either direction.

The observed value and change from baseline in DLQI/cDLQI score will also be summarized descriptively by study visit and treatment group using descriptive statistics in addition to the above noted model for the Double-blind Period.

8.2.5. Fissures

Fissuring will be assessed by recording the presence or absence of fissures, the number of fissures present, and the pain associated with each fissure. A fissure is a longitudinal and deep crack that separates the stratum corneum and may penetrate down to the dermis, causing pain and sometimes bleeding. The subject will assess pain associated with fissures as ranging from 0-3 (none, mild, moderate, severe).

The number and proportion of subjects with fissures present on palms or soles along with 95% CIs will be summarized by treatment group and study visit. A 2-sided Pearson's Chi-Square Test, or Fisher's Exact Test, as appropriate, will be performed at the 5% significance level to determine whether there is a significant difference between treatment groups. The null hypothesis that there is no difference in proportion of subjects with fissures present between active trifarotene cream HE1 and vehicle, with a 2-sided alternative considering a difference in either direction. The difference in proportions between active trifarotene cream HE1 and vehicle (active trifarotene cream HE1 minus vehicle), 95% CIs for the differences, and *P* values for the differences in treatment will also be presented.

The number of fissures and fissure pain level will be summarized descriptively by body area and treatment group.

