2.2.2.2. Secondary Efficacy Endpoints

The secondary efficacy endpoints of this study include the following:

- The difference in mean scores between the active trifarotene cream HE1 and vehicle groups in the following assessment indices from Baseline through Day 90:
 - 5-point Visual Index for Ichthyosis Severity (VIIS) for scaling (overall 16 points for scaling, i.e., 0-4 points for 4 body areas: chest/abdomen, back, arms, and legs)
 - Individual score for roughness (Scale: 0–4) overall
 - Palm/sole Assessment (Scale: 0–4)
 - Quality of life per Dermatology Life Quality Index (DLQI) and children’s DLQI (cDLQI)
- The difference in proportion of subjects with presence of fissures on palms/soles (presence/absence, number of fissures, and pain associated with fissures on a 0-3 scale) at Day 90 between the active trifarotene cream HE1 and vehicle groups

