3.1. Overall Design

This is a 2-cohort, multicenter study in subjects with moderate to severe LI (i.e., 3–4 on a 5-point Investigator’s Global Assessment [IGA] where 0 = clear; 1 = almost clear; 2 = mild; 3 = moderate; 4 = severe). Adults (Cohort A) and adults and adolescents (Cohort B) will be randomized in a double-blind fashion to 1 of 2 doses of trifarotene cream HE1 or vehicle and treated twice weekly for 90 days.

Approximately 15 adults (≥ 18 years old) will be randomized into the first cohort of subjects (Cohort A) in a 1:1:1 ratio to trifarotene cream HE1 100 $\mu\text{g/g}$, trifarotene cream HE1 200 $\mu\text{g/g}$, or vehicle and treated twice weekly for up to 90 days. After the initial 15 subjects complete at least 28 days of treatment, an independent data safety monitoring board (DSMB) will review aggregate safety and tolerability data.

If no safety issues are identified, both adults and adolescents (ages 12 to 17 years, inclusive) will be allowed to enroll in Cohort B. Subjects in Cohort B will be randomized 1:1:1 to trifarotene cream HE1 100 $\mu\text{g/g}$, trifarotene cream HE1 200 $\mu\text{g/g}$, or vehicle and treated twice weekly for up to 90 days in the same manner as subjects in Cohort A. All subjects (Cohort A and Cohort B) who complete the randomized, Double-blind Period of the study will be eligible to enter a 90-day, Open-label Extension (OLE) in which additional PK, safety, and efficacy data will be collected. Subjects in the OLE will receive open-label trifarotene cream HE1 200 $\mu\text{g/g}$ twice weekly for up to 90 days. A schematic of each period is provided in [Figure 1](#) and [Figure 2](#).

Figure 1: Double-blind Study Design

[figure not shown]
[figure not shown]

Figure 2: Open-label Study Design

The first cohort of 15 adult subjects is a reasonable sample size to assess safety and tolerability before enrolling adolescents. Accounting for a 20% drop-out/nonevaluable rate, a total sample size of 120 subjects randomized in a 1:1:1 ratio to 2 active trifarotene cream HE1 arms and a vehicle cream arm will provide >80% power to detect a difference between each separate trifarotene cream HE1 arm (32 evaluable subjects) and the vehicle cream arm (32 evaluable subjects) 2-sided Fisher's Exact Test assuming a 70% success rate and a 40% success rate, respectively. This study is not powered to detect a difference between the 2 active arms.

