4.1. Introduction

Data processing, tabulation of descriptive statistics, calculation of inferential statistics, and graphical representations will be performed primarily using SAS (release 9.4 or higher). If the use of other software is warranted, the final statistical methodology report will detail what software was used for what purposes.

Continuous (quantitative) variable summaries will include the number of subjects (n) with nonmissing values, mean, standard deviation (SD), standard error (SE), median, minimum, and maximum.

Categorical (qualitative) variable summaries will include the frequency and percentage of subjects who are in the particular category or each possible value. In general, the denominator for the percentage calculation will be based upon the total number of subjects in the study population for the treatment groups, unless otherwise specified. The denominator for by-visit displays will be the number of subjects in the relevant study population with nonmissing data at each study visit.

The minimum and maximum will be reported with the same degree of precision (i.e., the same number of decimal places) as the observed data. Measures of location (mean and median) will be reported to 1 degree of precision more than the observed data and measures of spread (SD, SE) will be reported to 2 degrees of precision more than the observed data.

Percentages will be presented to 1 decimal place, unless otherwise specified and with the following exceptions: a percentage of 0% will not be displayed (i.e., only the count of 0 will be displayed), and a percentage of 100% will be displayed with 0 decimal places.

Unless otherwise indicated, all statistical tests will be conducted at the 0.05 significance level using 2-tailed tests, and *P* values will be reported. Corresponding 95% confidence intervals (CIs) will be presented for statistical tests. A *P* value of ≤ 0.10 but > 0.05 will be considered evidence of a trend.

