6.1.2. Adjustments for Covariates

If there is a statistical difference among treatment groups with respect to baseline characteristics, that variable may be added to the statistical models as a blocking factor or covariate to determine the effect on treatment. Age group and baseline score are planned for inclusion in statistical models, unless otherwise indicated. Age group will be categorized as adolescents (ages 12 to 17 years, inclusive) and adults (≥ 18 years).

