6.1.3. Multiple Comparisons

No adjustments will be made for multiple comparisons. All *P* values for the secondary and exploratory endpoints will be provided in the summary tables for informational purposes only.

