No Fissures Present	XX (XX.X%)	XX (XX.X%)	XX (XX.X%)	XX (XX.X%)
Comparison vs. Vehicle				
Difference in Percentage of Fissures Present	XX.X	XX.X	XX.X	
95% CI for Difference in Percentage of Fissures Present	(XX.X, XX.X)	(XX.X, XX.X)	(XX.X, XX.X)	
P value for Difference	X.XXXX	X.XXXX	X.XXXX	
...				
Day 90				
Fissures Present	XX (XX.X%)	XX (XX.X%)	XX (XX.X%)	XX (XX.X%)
No Fissures Present	XX (XX.X%)	XX (XX.X%)	XX (XX.X%)	XX (XX.X%)
Comparison vs. Vehicle				
Difference in Percentage of Fissures Present	XX.X	XX.X	XX.X	
95% CI for Difference in Percentage of Fissures Present	(XX.X, XX.X)	(XX.X, XX.X)	(XX.X, XX.X)	
P value for Difference	X.XXXX	X.XXXX	X.XXXX	

Abbreviations: CI = confidence interval; ITT = intent-to-treat.

Note: Percentages are n/Number of subjects in the ITT population within randomized treatment group*100.

[1] P value from 2-sided Pearson's Chi-Square test. Difference is calculated Trifarotene cream HE1 - vehicle.

[2] Baseline is defined as the last non-missing assessment recorded prior to the first dose of treatment in the Double-blind Period.

SOURCE: Listing 16.2.6.6

Programming Note: If cell counts are <5, use Fisher's Exact Test and update footnote [1] accordingly. Include all study visits (Days 14, 30, and 60).

Table 14.2.6.1.2
Presence of Fissures on Palms or Soles
OLE ITT Population

Study Visit Category/Statistic	Trifarotene cream HE1 200 ug/g
Baseline [1]	
Fissures Present	XX (XX.X%)
No Fissures Present	XX (XX.X%)
Day 104	
Fissures Present	XX (XX.X%)
No Fissures Present	XX (XX.X%)
Day 120	
Fissures Present	XX (XX.X%)
No Fissures Present	XX (XX.X%)
Day 150	
Fissures Present	XX (XX.X%)
No Fissures Present	XX (XX.X%)
Day 180	
Fissures Present	XX (XX.X%)
No Fissures Present	XX (XX.X%)
Day 194	
Fissures Present	XX (XX.X%)
No Fissures Present	XX (XX.X%)

Abbreviations: CI = confidence interval; ITT = intent-to-treat; OLE = open label extension.

Note: Percentages are n/Number of subjects in the OLE ITT population within treatment group*100. All subjects received Trifarotene cream HE1 200 ug/g in the OLE.

[1] Baseline is defined as the last non-missing assessment recorded prior to the first dose of treatment in the Double-blind Period.

SOURCE: Listing 16.2.6.6

Table 14.2.6.2.1
Secondary Analysis: Summary of Number of Fissures and Fissure Pain Level
ITT Population

Body Area: Palms				

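### The Day 90 fissure comparison ignores recorded baseline fissure status: the test is valid, but adjusting is a free improvement that can recover power and remove chance baseline imbalance

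*SAP*

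**What the plan says.** SAP 2.2.2.2 sets the secondary endpoint as "The difference in proportion of subjects with presence of fissures on palms/soles" at Day 90, active against vehicle. It is a status at one visit, not a change.

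SAP 8.2.5 tests "The null hypothesis that there is no difference in proportion of subjects with fissures present between active trifarotene cream HE1 and vehicle". The method is a two-sided Pearson "Chi-Square Test, or Fisher's Exact Test, as appropriate, will be performed at the 5% significance level", with the difference in proportions and its 95% CI. The shell for Table 14.2.6.1.1 adds "If cell counts are <5, use Fisher's Exact Test and update footnote [1] accordingly". There is no baseline term, stratification or at-risk subset.

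The baseline value exists. Table 1 schedules the palm/sole fissuring assessment at Screening and Baseline, and Table 14.2.6.1.1 has a Baseline row for fissures present and absent.

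Elsewhere the plan adjusts. SAP 6.1.2 states "Age group and baseline score are planned for inclusion in statistical models, unless otherwise indicated". The logistic models for IGA success and 50% IGA reduction (8.1.1), 2-grade roughness change (8.2.2) and 2-grade palm/sole change (8.2.3) all include the corresponding baseline score and age group. On the standing of the result, 6.1.3 says that P "values for the secondary and exploratory endpoints will be provided in the summary tables for informational purposes only".

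**The concern.** Fissure presence is the only binary efficacy endpoint compared between arms without its baseline value, and 8.2.5 gives no reason. SAP 3.1 describes entry by IGA grade 3 to 4, and 8.1.1 excludes palms and soles from the IGA, so some subjects may well enter without fissures. The baseline shell provides a row for them. They can only stay clear or worsen, and at Day 90 a subject who never had a fissure counts the same as one whose fissures healed.

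Two consequences follow. A healing effect among those with fissures is diluted in the whole-arm contrast. A chance difference in baseline prevalence also carries through to the reported Day 90 difference, to the extent that fissures persist. With 65 subjects enrolled instead of 120, such differences are larger. Clearance and new onset are not tabulated, so a reader could not separate them.

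**Working it through.** **Plan's figure.** The SAP states no power, prevalence or expected effect for fissures. Its only power statement concerns the IGA endpoint and does not bear on this point.

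**Inputs from the SAP.** Subjects are "randomized in a 1:1:1 ratio to 2 active trifarotene cream HE1 arms and a vehicle cream arm"; 32 evaluable per arm were planned; 65 were enrolled, and 65/3 = 21.7, so about 21 to 22 per arm before dropout. On the level, "all statistical tests will be conducted at the 0.05 significance level using 2-tailed tests".

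**Assumed inputs.** Prevalence at entry 30% to 90%; vehicle persistence (present at Day 90 if present at baseline) 60% to 90%; vehicle onset (present at Day 90 if absent at baseline) 5% to 40%; active treatment lowers persistence to between half and five-ninths of the vehicle value.

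**Step 1: dilution.** Take prevalence 50%, persistence 90% (vehicle) and 50% (active), onset 10% in both.
- Vehicle: 0.5 × 0.90 + 0.5 × 0.10 = 50%.
- Active: 0.5 × 0.50 + 0.5 × 0.10 = 30%.
- The 40-point effect in subjects with baseline fissures becomes 20 points in the whole arm.

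**Step 2: chance imbalance.** At 21 per arm and 50% prevalence, the SD of the baseline difference is sqrt(2 × 0.25/21) = 15.4 points. Multiplied by persistence minus onset (0.90 - 0.10 = 0.80), this puts an SD of 12.3 points into the Day 90 difference when there is no effect. By exact binomial calculation, the two arms differ at baseline by more than 15 points in about 28% of trials.

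**Step 3: how much baseline explains.** The share of vehicle-arm Day 90 variance explained is π(1-π)(persistence - onset)² / [p(1-p)], where π is prevalence and p the Day 90 proportion. At π = 50% it is 72% for persistence/onset 90/5, 49% for 80/10, 25% for 70/20 and 4% for 60/40.

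**Step 4: power at 32 per arm, 50% prevalence.** Simulation, 20,000 trials per scenario; CMH is stratified by baseline fissure presence.

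| Vehicle persistence/onset | Active | Crude chi-square | CMH |
|---|---|---|---|
| 90/5 | 50/5 | 39% | 62% |
| 80/10 | 40/5 | 49% | 64% |
| 70/20 | 35/10 | 49% | 55% |
| 60/40 | 30/20 | 56% | 55% |

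At 90% prevalence the change is -2 to +6 points in these four scenarios. Over prevalence 30% to 90% the extremes are 66.0% - 68.1% = -2 points and 62.0% - 39.2% = +23 points.

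**Step 5: power at 21 per arm, Step 1 scenario.** The planned rule is read as Fisher when any observed cell is below 5.
- Crude chi-square throughout: 26%.
- Planned rule: 21%.
- CMH: 39%.

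Of the 18 points between planned rule and CMH, about 5 (26 - 21) come from the switch to Fisher and about 13 (39 - 26) from using baseline. At 32 per arm the same scenario gives 39% against 55%.

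**Step 6: validity.** With no treatment effect at 21 per arm, the planned rule rejects in about 4.2% of trials and CMH in about 3.6%. Across the null scenarios at 21 to 40 per arm, crude chi-square rejects in 4.6% to 5.8% and crude Fisher in about 2% to 3%.

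**The case against.** The defence is strong on several points. Randomisation balances baseline status in expectation, and the crude P value and interval already allow for chance imbalance, so nothing is invalid. The test matches the endpoint in 2.2.2.2, which is presence at Day 90. SAP 6.1.2 is not breached: it concerns models and allows exceptions, and a chi-square test is not a model. Secondary P values are informational. The Baseline row makes imbalance visible, and the palm/sole score, whose grades include fissures, already has baseline-adjusted analyses. The entry criteria are known here only as the SAP describes them. All of this stands.

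A reader might go further and infer that the comparison mostly measures who had fissures at entry, or that it necessarily loses much of its power. The documents support neither. Baseline dominates the outcome only if fissures are very persistent, and the SAP says nothing on persistence or prevalence. With 60% persistence and 40% onset there is no gain at 32 per arm.

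What the defence does not answer is why a recorded and probably prognostic value is left out here when every comparable endpoint uses it. Seeing an imbalance in a table does not remove it from the estimate.

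**Conclusion.** The point holds as one of efficiency and consistency, not as an error. The crude comparison is valid but can lose power, and it leaves chance baseline imbalance in the estimated difference. Under the assumed ranges, stratifying changes power by about -2 to +23 points at 32 per arm: most when fissures persist and about half of subjects have them at entry, near zero when fissures come and go, and little when nearly all have them. At about 21 per arm the persistent scenario gives about 21% against 39%, with about 5 of those points due to Fisher's conservatism. Every one of these figures depends on prevalence, persistence, onset and effect values that the SAP does not supply. This is a free improvement to an informational secondary analysis.

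**What to change.** In 8.2.5 and Table 14.2.6.1.1, base the treatment comparison on one of:
- the plan's logistic model with treatment, baseline fissure presence (yes/no) and age group, using Firth estimation under separation as elsewhere; or
- a Cochran-Mantel-Haenszel test with a risk difference stratified by baseline fissure presence.

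Keep the crude percentages and crude difference as descriptive. Add two rows by arm: clearance among subjects with fissures at baseline, and new fissures among those without.

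The cost is SAP wording, one table shell and its programming. No new data are needed. SAP section 1 says the plan is filed before any unblinded analysis, so the choice should be fixed before then.
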